response. Patients with GST scores higher than 10 ng/ml will not be included in the treatment study, but may be asked to collect a single fecal sample (omnigene and viable).

See Protection of Human Subjects - Recruitment Methods and Consenting Process for detailed information regarding recruitment and consenting.

Experimental Protocol.

mTBI Group (Arm 1)

Before and at completion (month 6) of the rhGH intervention, mTBI subjects will report to the UTMB Institute for Translational Sciences (ITS) Clinical Research Center (CRC) for testing, which will consist of cognitive function assessment (MoCA), determination of brain morphology and connectivity using fMRI, determination of lean mass and fat mass using DEXA, resting energy expenditure, functional testing including leg strength and 6 minute walk test, fatigue measurements, and questionnaires of mood and quality of life, gastrointestinal health, sleep, and food preferences. Blood sampling for measurement of amino acid levels, hormones, and metabolites will be drawn before and 90 minutes (+/- 10 minutes) after a standardized meal. In addition, fecal samples for analysis of the GI microbiome will be collected monthly for the duration of the study. Insulin Growth Factor 1 (IGF-1) levels will be monitored at a month 1 safety visit for all mTBI subjects. The month 1 safety visit will occur +/- 5 days from the expected date based on the baseline study visit. The monthly fecal sampling will occur +/- 7 days from the expected date based on the baseline study visit. The month 6 post study will occur +/- 7 days from the expected date based on the baseline study visit. A member of the study team will contact the subject each month to coordinate fecal sample transport to UTMB, check for adverse events and overall well-being, and ensure compliance and ongoing consent. If a mTBI subject sustains an additional TBI during the study, the study for both the mTBI and household control subject will be extended to collect monthly fecal samples and questionnaires for an additional 6 months. Genotropin will be provided for the additional 6 months.

Household control group (Arm 1)

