GENOTROPIN (5 mg) is dispensed in a two-chamber cartridge. The front chamber contains recombinant somatropin (5.8 mg), glycine (2.2 mg), mannitol (1.8 mg), sodium dihydrogen phosphate anhydrous (0.32 mg), and disodium phosphate anhydrous (0.31 mg); the rear chamber contains 0.3% m-Cresol (as a preservative) and mannitol (45 mg) in 1.14 mL water for injection. The reconstituted concentration is 5 mg/ml. GENOTROPIN will be administered utilizing the GENOTROPIN Pen 5 (manufactured by Pfizer, Inc). The GENOTROPIN Pen 5 is a reusable multi-dose pen that the two-chambered cartridge is inserted into. Once the cartridge is inserted into the pen, the two-chambers are mixed. A 31 gauge, ½ inch needle is attached to the pen for administration. The pen can then be dialed on the digital display to the correct dose and administered by the user. The needle is then carefully removed and disposed in a sharps medical waste container provided by the study team. Once the cartridge is empty, a new cartridge can be inserted into the pen, a 5 mg cartridge will last 1 – 2 weeks depending on the dose used. The GENOTROPIN Pen 5 is designed to be easily used, as most GH replacement is for pediatric use. Subjects will undergo a familiarization session with the study team to learn how to load the GENOTROPIN5 cartridges into the GENOTROPIN Pen 5 device, how to dial their dose, and how to administer injections. They will also be given a guide and the web address (<http://www.genotropin.com/genotropin-helpful-tools>) of a video prepared by the makers of GENOTROPIN to take home for reference.

In this study, single injections containing 0.4 mg of GENOTROPIN will be administered to mTBI and PASC subjects on a daily basis until the IGF-1 safety check at month 1. If the IGF-1 value is less than 400 ng/mL, the subject will be directed to increase the dose to 0.6 mg per day for the remainder of the study. 0.6 mg per day is the standard dose given in our TBI research studies. We have treated approximately 60 TBI research subjects over approximately 14 years at this dose without incident. [name] also has approximately 100 patients in his clinic being treated at 0.6

mg per day. At this dose of GH replacement, there is no evidence of insulin resistance and as long as the IGF-1 remains at or below 400 ng/mL, there is minimal risk of carpal tunnel syndrome.

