- Recombinant Human Growth Hormone Administration. mTBI and PASC subjects will be asked to inject themselves with growth hormone daily. The starting dose will be 0.4 mg/day beginning at the baseline study and will increase to 0.6 mg/day when instructed by the study team. The dose increase will happen after the month 1 IGF-1 blood draw and the study team reviews the results and instructs the subject to increase their dose to 0.6 mg/day. TBI subjects will administer growth hormone for 6 months. PASC subjects will administer growth hormone for 9 months. If a mTBI subject sustains an additional TBI during the study period, the study will be extended for an additional 6 months. Genotropin will be provided for the additional 6 months at a dose of 0.6 mg/day.
- Glucagon stimulation test. Arm 3 PASC subjects will have a glucagon stimulation test at month 12. After the IV is placed, 3.5 ml of blood will be collected for the baseline (time: 0 minutes) to test for levels of human growth hormone. 1 mg glucagon (for subjects over 90 kg, 1.5 mg glucagon) will be injected IM in the deltoid muscle of the subject. Additional blood samples (3.5 mL) will be collected to test for levels of human growth hormone at time points: 90 minutes, 120 minutes, 150 minutes, and 180 minutes. All blood samples will be sent to UTMB clinical laboratory for analysis and entered into subjects UTMB medical chart.

Study Procedures for household and healthy control subjects.

Household controls will complete the procedures below. Differences in procedures between Arm 1 and Arm 2 will be noted.

- Vital signs. Vital signs will be collected at all study visits. This will include height, weight, blood pressure, pulse, respirations, and temperature. Vital signs will be recorded on the appropriate study visit CRF.
- Blood draw. Subjects will have blood drawn at the baseline (month 0) and post (month 6) visits. Blood will be drawn using a butterfly needle from a peripheral vein in the arm. Subjects will be fasted for at least 10 hours.
 - Baseline Visit (Month 0):
Up to 15 ml of blood (1 serum separator top (5ml); 1 lithium heparin (6ml); 1 K-EDTA (4ml)) will be collected from fasted (at least 10 hours) subjects for analysis of hormones, amino acids and metabolites. In addition, up to 13ml of blood (1 serum separator top (5ml); 1 lithium heparin (6ml)) will be collected after a standardized meal for the analysis of amino acids.
 - Post Visit (Month 6):

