Glucagon Stimulation Testing. The known side effects of the glucagon stimulation test are headache and nausea and possible vomiting.

Electrocardiogram (EKG). This is a non-invasive, painless test. There is a risk of irritation or a rash on the skin from the electrodes.

DEXA scan. The measurement of lean and fat mass by DEXA involves a brief exposure (~15 min) to a low dose of radiation (~ 0.05 mrem/whole body scan), calculated to be approximately equal to a 2 h airplane flight per scan. Otherwise, there are no known risks of measuring body composition.

Indirect calorimetry. There are no known risks involved with these measurements.

Magnetic Resonance Imaging (MRI) (Arm 1 only). As MRI is a procedure that does not involve radiation and is non-invasive, the main risks are accidental injury resulting from the presence of metal objects on one's clothes or person (e.g. jewelry, piercings, implants, pacemakers, some types of tattoos, IUDs). In addition, some individuals may experience claustrophobia due to the confined space within the scanner.

Cognitive Testing. There are no known risks involved with this testing.

Fecal Sampling. There is no known risk of this procedure.

Nasal Swab. Risks include momentary pain and a chance for minor bleeding from the nose similar to the risks associated with nasopharyngeal SARS-CoV-2 testing.

Performance testing and 6-minute walk. The exercise tests may cause muscle soreness, cramps, dizziness, and possibly irregular heartbeats. The risks of the 6-minute walk include falling, elevated heart rate and elevated blood pressure. All subjects will be accompanied by a trained staff member.

Questionnaires. There is no known risk to completing the questionnaires listed in this study.

Recombinant Human Growth Hormone (rhGH). The potential risks of taking growth hormone include weight gain, joint pain, and increased blood glucose. In addition, Carpal Tunnel Syndrome, a condition characterized by numbness or pain in the wrists and fingers, has been associated with growth hormone therapy. These effects are modifiable with dose adjustment and are unlikely due to the relatively brief period of time that patients will be receiving growth hormone during the course of the study. An IGF-1 lab will be drawn at the 1-month time point. If the IGF-1 value is over 400 ng/ml, the dose of GH will not be increased.

Confidentiality. Divulgation of personal sensitive data is a general risk of clinical investigations involving human subjects.

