Magnetic Resonance Imaging. Subjects will be screened for the presence of implanted medical devices, embedded metal or other material for which MRI is contraindicated according to standard UTMB safety guidelines. To protect against loud noises, participants will wear foam earplugs and / or headphones to reduce the loud noises made by the scanner. To reduce claustrophobia, subjects will be able to talk to investigators throughout the study via intercom, and will be able let us know right away if they want to stop the study and get out of the scanner.

Fecal Sampling. There are no known risks of this procedure.

Nasal Swab. Care will be taken to minimize pain and/or bleeding.

Performance testing and 6-minute walk. Risk of muscle soreness or cramps can be reduced or avoided with an adequate warm-up. The subjects will be accompanied by a qualified staff member at all times.

Questionnaires. There are no known risks of this procedure.

Recombinant Human Growth Hormone Administration. The potential risks of taking growth hormone (weight gain, increased blood glucose, joint pain, and Carpal Tunnel Syndrome), will be described in the consent form. These effects are unlikely due to the relatively brief period of time that subjects will be receiving growth hormone during the course of the 6 or 9-month treatment period. An IGF-1 lab will be drawn at the 1-month time point. If the IGF-1 value is over 400ng/ml, the dose of GH will not be increased.

Confidentiality. Only the investigators, the study personnel, and the Medical Records department of the UTMB Hospital will have access to the subjects' personal information. All data containing the name of the patients will be locked in the PI office. To preserve confidentiality, immediately after enrollment each subject will be assigned a code by which each research sample will be identified for further analysis, thus avoiding identification by non-qualified individuals.

C. Potential Benefits of the Proposed Research to the Subjects and Others

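### The re-injury extension fixes the dose at 0.6 mg/day for every mTBI subject, including any whom the IGF-1 rule holds at 0.4 mg/day

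*Combined protocol and SAP*

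**What the plan says.** **Main-period dose.** The Therapeutic Intervention section starts mTBI and PASC subjects at 0.4 mg/day until the month 1 IGF-1 check. The condition for an increase reads: "less than 400 ng/mL, the subject will be directed to increase the dose to 0.6 mg per day for the remainder of the study". The same section explains the threshold: "as long as the IGF-1 remains at or below 400 ng/mL, there is minimal risk of carpal tunnel syndrome".

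**When IGF-1 is high.** The rhGH paragraph under Potential Risks states: "If the IGF-1 value is over 400 ng/ml, the dose of GH will not be increased". The rhGH paragraph under Protections against risks repeats it: "If the IGF-1 value is over 400ng/ml, the dose of GH will not be increased". A subject above the threshold therefore stays at 0.4 mg/day.

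**The increase in the administration bullet.** In the study procedures, the Recombinant Human Growth Hormone Administration bullet says the dose "will increase to 0.6 mg/day when instructed by the study team", after the team has reviewed the month 1 IGF-1 result. That is consistent with the rule above and is not in dispute.

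**The extension.** If an mTBI subject has another TBI during the study, the Arm 1 and Arm 2 descriptions in the Experimental Protocol share this wording: "will be extended to collect monthly fecal samples and questionnaires for an additional 6 months. Genotropin will be provided for the additional 6 months". They give no dose. The administration bullet does: "Genotropin will be provided for the additional 6 months at a dose of 0.6 mg/day". It is the only place in the document that names an extension dose.

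**The concern.** The main-period rule has two branches: 0.6 mg/day if IGF-1 is below 400 ng/mL, and no increase if it is above. The extension sentence has only one. For a subject already on 0.6 mg/day this makes no difference. For a subject kept at 0.4 mg/day because IGF-1 was high, following the extension sentence means raising the dose, and following the two risk paragraphs means not raising it.

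What is at stake is patient safety on a small scale. The protocol ties minimal carpal tunnel risk to IGF-1 staying at or below 400 ng/mL, and withholding the increase is the concrete protection it offers. The literal sentence removes that protection from exactly the subjects it was written for. It does so in a period with little laboratory cover: the Blood draw section schedules no mTBI draw after month 6, and no dose rule is attached to the IGF-1 measured at month 6. The protections section also reassures on the ground that exposure is brief, citing a 6- or 9-month treatment period. An additional 6 months takes an mTBI subject beyond the planned 6-month course.

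**Working it through.** The plan gives no figure to reproduce here. The check sets the dosing texts side by side and then sizes the difference.

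**1. Dose by IGF-1 result**

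| Month 1 IGF-1 | Dose under Therapeutic Intervention, Potential Risks and Protections against risks | Extension dose in the administration bullet | Agree? |
|---|---|---|---|
| Below 400 ng/mL | 0.6 mg/day for the rest of the study | 0.6 mg/day | Yes |
| Over 400 ng/mL | No increase, so 0.4 mg/day | 0.6 mg/day | No |

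No section adds an exception or an IGF-1 condition for the extension. (A value of exactly 400 ng/mL meets neither the condition for increasing nor the condition for withholding. That is a separate wording gap.)

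**2. Does the main-period rule reach into the extension?** Therapeutic Intervention sets the dose for the remainder of the study. The Experimental Protocol and the administration bullet both describe the extra 6 months as the study being extended. The rule can therefore be read as still in force, and on that reading the fixed 0.6 mg/day contradicts it for a held subject.

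**3. Size per affected subject (literal reading)**

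- Ratio: 0.6 / 0.4 = 1.5, which is 50% higher.
- Length: 365.25 / 2 = 182.6 days.
- At 0.4 mg/day: 0.4 × 182.6 = 73.1 mg.
- At 0.6 mg/day: 0.6 × 182.6 = 109.6 mg.
- Difference: 109.6 − 73.1 = 36.5 mg.

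**4. Number of subjects affected**

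A subject is affected only if the increase was withheld (probability p) and a further TBI occurs on study (probability q). The planned number of mTBI subjects is 50 (25 in each of Arms 1 and 2). PASC subjects are outside this provision and controls receive no drug. The documents give neither p nor q, so the values below are assumptions, with the two events taken as independent.

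Expected number = 50 × p × q. Chance of at least one = 1 − (1 − p × q)^50.

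| Assumed p = q | p × q | Expected number | Chance of at least one |
|---|---|---|---|
| 2% | 0.0004 | 0.02 | 1 − 0.9996^50 = 0.020 |
| 5% | 0.0025 | 0.125 | 1 − 0.9975^50 = 0.118 |
| 10% | 0.01 | 0.5 | 1 − 0.99^50 = 0.395 |

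The last row needs both rates at the top of the assumed range.

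**The case against.** **The rule carries over, so this is shorthand.** The administration bullet is terse throughout. It does not state the 400 ng/mL threshold for the main period either, and the only route it describes from 0.4 to 0.6 mg/day is IGF-1 review followed by instruction. The extension sentence comes after that, and it speaks of providing drug rather than of raising a dose. On this view 0.6 mg/day is just the usual maintenance dose, still subject to the hold. The reading is plausible, and a careful team might well follow it. But the sentence names a fixed dose and nothing in the document says the hold applies to it. The main-period increase is explicitly conditional on review and instruction, and the extension dose is not.

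**The hold concerns month 1 only.** In both risk paragraphs the rule directly follows a sentence about the 1-month draw, so it may govern that decision alone. The extension would then be a gap, not a contradiction. This weakens any claim that those two paragraphs apply indefinitely. It does not rescue the sentence, because Therapeutic Intervention sets its dose for the remainder of a study that the plan itself extends. Even on the gap reading, a subject held back for safety would be moved to the higher dose with no check.

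**Other safeguards exist.** IGF-1 is redrawn at month 6. Investigators monitor laboratory values and rhGH treatment, data are reviewed weekly, and staff contact subjects monthly about adverse events. The protocol says of the side effects: "These effects are modifiable with dose adjustment". It also reports about 60 TBI research subjects treated at 0.6 mg/day without incident, and about 100 clinic patients on that dose. All of this lowers the risk. None of it corrects the instruction, and the earlier experience is not specific to people with IGF-1 over 400 ng/mL.

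**Almost nobody is affected.** This stands, and it is why the point is minor.

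**Conclusion.** The concern holds. The only sentence that sets an extension dose sets the wrong one for a re-injured mTBI subject whose increase was withheld: 0.6 instead of 0.4 mg/day, 50% higher for up to 6 months. It is a stated dose that conflicts with a stated safety rule, not merely a missing detail.

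Its practical weight is small. Under assumed rates of 2% to 10% for each of the two events, the expected number affected is below one, so probably few or none. That range rests entirely on the assumed rates and on independence. The inconsistency itself rests only on the text. There is no consequence for power or for any endpoint.

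**What to change.** In the Recombinant Human Growth Hormone Administration bullet, replace the fixed extension dose with: *at the subject's current dose (0.4 or 0.6 mg/day, according to the IGF-1 rule in the Therapeutic Intervention section)*.

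The cost is a few words in one sentence, with no added visits, tests or subjects, and nothing changes for anyone already on 0.6 mg/day. The edit restores the dose hold. It does not add IGF-1 monitoring during the extension, which would be a separate decision.

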analysis of the GI microbiome will be collected monthly for the duration of the study. Insulin Growth Factor 1 (IGF-1) levels will be monitored at a month 1 safety visit for all PASC subjects. The month 1 safety visit will occur +/- 5 days from the expected date based on the baseline study visit. The fecal sampling will occur +/- 7 days from the expected date based on the baseline study visit at months 0, 1, 2, 3, 4, 5, 6, 9 and 12. The month 6 study will occur +/- 7 days from the expected date based on the baseline study visit. The month 9 study will consist of fecal sample and questionnaires only. At month 12, the subject will return to the ITS-CRC to repeat the glucagon stimulation test (GST). Questionnaires and a fecal sample will also be collected at this time. A member of the study team will contact the subject each month to coordinate fecal sample transport to UTMB, check for adverse events and overall well-being, and ensure compliance and ongoing consent. If a PASC subject is infected with COVID again during the study months 9 - 12, the study will be extended to collect fecal samples and questionnaires for an additional 3 months.

Therapeutic Intervention (for mTBI subjects only - Arms 1&2; PASC subjects – Arm 3). Recombinant human growth hormone (rhGH), (GENOTROPIN). Growth hormone (GH) is produced endogenously by the body and is released by the pituitary. Therapeutic rhGH is FDA approved for clinical use for replacement of endogenous growth hormone in children and adults with growth hormone deficiency. GENOTROPIN, the agent to be used in this study is manufactured by Pfizer Inc and contains somatropin, which is a polypeptide hormone of recombinant DNA origin. It contains 191 amino acid residues and is identical to human growth hormone of pituitary origin.

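### The fixed 0.6 mg/day dose for the mTBI re-injury extension conflicts with the IGF-1 hold for any subject kept at 0.4 mg/day (wrong as written, minor)

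*Combined protocol and SAP*

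**What the plan says.** All references are to the combined protocol and SAP.

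- **Increase rule.** The Therapeutic Intervention section starts mTBI and PASC subjects at 0.4 mg/day and makes the increase conditional on the month 1 safety check: "If the IGF-1 value is less than 400 ng/mL, the subject will be directed to increase the dose to 0.6 mg per day".
- **Hold rule.** The growth hormone item under Potential Risks says "If the IGF-1 value is over 400 ng/ml, the dose of GH will not be increased". The matching item under Protections against risks repeats it: "If the IGF-1 value is over 400ng/ml, the dose of GH will not be increased". A subject over the threshold therefore stays at 0.4 mg/day.
- **Reason for the threshold.** The Therapeutic Intervention section gives it: "as long as the IGF-1 remains at or below 400 ng/mL, there is minimal risk of carpal tunnel syndrome".
- **Extension, design text.** For Arms 1 and 2, the Experimental Protocol section says that after a further TBI follow-up "will be extended to collect monthly fecal samples and questionnaires for an additional 6 months. Genotropin will be provided for the additional 6 months". No dose is given.
- **Extension, dosing text.** The Recombinant Human Growth Hormone Administration item under the study procedures for treated subjects supplies the dose: "Genotropin will be provided for the additional 6 months at a dose of 0.6 mg/day". No IGF-1 condition is attached.
- **Arm 3.** The PASC reinfection extension differs: "the study will be extended to collect fecal samples and questionnaires for an additional 3 months". It adds no drug.

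**The concern.** The protocol creates a group of subjects held at the lower dose for a stated safety reason, and then sets a single dose for the extension that does not recognise that group. Someone dosing from the administration item would give a held, re-injured subject 0.6 mg/day. Someone dosing from the risk sections would keep that subject at 0.4 mg/day.

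At stake is the exposure of a subject whose IGF-1 was already over 400 ng/mL on the lower dose. The protocol's reassurance about carpal tunnel syndrome is worded for IGF-1 at or below 400, so it does not cover this subject. Protections against risks also calls the side effects unlikely because treatment is short, at 6 or 9 months. With the extension an mTBI subject could be treated for 6 + 6 = 12 months.

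**Working it through.** The plan gives no figure to reproduce here. The check sets the dosing rules side by side and then works out the dose difference.

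**1. Rules applied to the two kinds of subject**

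| Subject at month 1 | Dose to month 6 | Extension dose as written | Change |
|---|---|---|---|
| IGF-1 below 400 ng/mL | 0.6 mg/day | 0.6 mg/day | none |
| IGF-1 over 400 ng/mL | 0.4 mg/day (held) | 0.6 mg/day | increase |

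Only the second row conflicts with the hold rule.

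**2. Does any other text settle it?**
- The Arm 1 and Arm 2 design text promises extension drug but names no dose.
- Both statements of the hold follow directly on the month 1 draw. Nothing says the hold lapses, and nothing says it carries into the extension.
- The same administration item does tie the first increase to a decision: the dose "will increase to 0.6 mg/day when instructed by the study team", after the team has seen the month 1 result. The extension sentence contains no such step.

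**3. Would a blood test catch a further rise?** The blood-draw schedule for mTBI subjects lists baseline, month 1 and month 6; month 12 is for PASC only. The extension lists fecal samples and questionnaires. Taking the extension to follow month 6, which is how I read it, the last scheduled IGF-1 in a held subject is drawn on 0.4 mg/day, and none is drawn on 0.6 mg/day.

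**4. Size per affected subject**
- Ratio: 0.6 / 0.4 = 1.5, so +50%.
- Difference: 0.6 − 0.4 = 0.2 mg/day.
- Six months taken as 365 / 2 = 182.5 days.
- At 0.4 mg/day: 0.4 × 182.5 = 73 mg.
- At 0.6 mg/day: 0.6 × 182.5 = 109.5 mg.
- Extra drug: 109.5 − 73 = 36.5 mg.

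**5. How many subjects.** The ceiling is all mTBI subjects, 25 + 25 = 50. A subject is affected only if month 1 IGF-1 exceeded 400 ng/mL and another TBI occurred during the study. The documents give neither rate, so no expected number can be computed.

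**6. With the corrected wording.** A held subject stays at 0.4 mg/day (change 0) and everyone else stays at 0.6 mg/day.

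**The case against.** The best defence is that the administration item should be read whole. It makes the increase depend on an instruction from the study team after reviewing IGF-1, and a held subject never received that instruction. To reach 0.6 mg/day in the extension, the team that imposed the hold would have to override a rule stated twice with no end date. The Therapeutic Intervention section calls 0.6 mg/day the standard dose in this group's TBI studies, so the extension sentence may simply name the usual maintenance dose. This has force: a reader might infer that held subjects would certainly be escalated, or that the sponsor intends it, and the documents support neither. The defence does not remove the mismatch, because it needs a rule imported from the risk sections to limit a sentence that is unconditional as written.

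A second defence concerns oversight. The Data Safety and Monitoring Plan has the investigators follow lab values and growth hormone treatment throughout, with weekly data review. The team contacts subjects monthly to arrange sample transport and ask about adverse events, and since monthly sampling continues in the extension, those contacts presumably do too. Potential Risks describes the side effects as modifiable by changing the dose. So it would be wrong to infer six months without safety oversight. What stands is narrower: none of these measures schedules an IGF-1 test.

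A reader might also want to extend the point to PASC subjects, whose month 6 IGF-1 is drawn before their last three treatment months with no written dose rule attached. That contradicts no stated rule. The result is already drawn and falls under investigator monitoring, so asking for a recorded decision is a preference about documentation.

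**Conclusion.** Wrong as written, minor. The extension sentence conflicts with the IGF-1 hold for any re-injured mTBI subject kept at 0.4 mg/day. Followed literally, it gives that subject a 50% higher dose for six months without a scheduled IGF-1 measurement.

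The wording conflict is certain; whether anyone would be escalated is not. The number affected is probably small and possibly zero, because it needs two events together. The finding rests on the literal text, on the extension following month 6, and on the absence of any statement about whether the hold continues.

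A reader might infer that the trial's results are at risk. They are not: no endpoint, power figure or month 0 to month 6 comparison changes.

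**What to change.** In the Recombinant Human Growth Hormone Administration item, replace the fixed 0.6 mg/day for the extension with: *at the subject's current dose (0.4 mg/day if the increase was withheld for IGF-1 over 400 ng/mL)*.

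Optionally, state the 400 ng/mL condition for the month 1 increase in the same item, so that it agrees with the Therapeutic Intervention, Potential Risks and Protections against risks text.

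The cost is one phrase, or two. It needs no new visit, sample, blood volume or subjects. Subjects already on 0.6 mg/day are unaffected, and a held subject uses less drug than under the present wording. If 0.6 mg/day was only shorthand, the change states what was meant.
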